### **10.3 PREGNANCY**

If a patient becomes pregnant during the study or within 30 days of discontinuing study drug, the Investigator will report the pregnancy to [REDACTED] within 24 hours of being notified (see Section 10.6.1 for contact information). [REDACTED] will then forward the Exposure In Utero form to the Investigator for completion.

A patient who becomes pregnant while on study drug will immediately be withdrawn from the study and ET study procedures will be performed.

The patient will be followed by the Investigator until completion of the pregnancy. If the pregnancy ends for any reason before the anticipated date, the Investigator will notify [REDACTED]

At the completion of the pregnancy, the Investigator will document the outcome of the pregnancy. If the outcome of the pregnancy meets the criteria for immediate classification as an SAE (i.e., postpartum complication, spontaneous abortion, stillbirth, neonatal death, or congenital anomaly), the Investigator will follow the procedures for reporting an SAE (see Section 10.6).

#### **10.4 PATIENT WITHDRAWAL**

If a patient experiences an AE that leads to discontinuation of study drug treatment and/or withdrawal from the study, the eCRF will identify the AE as the reason for study drug discontinuation or withdrawal.

#### **10.5 SERIOUS UNEXPECTED SUSPECTED ADVERSE REACTIONS**

According to FDA CFR 312.32(a), FDA Guidance “Safety Reporting Requirements for Investigational New Drugs (INDs) and Bioavailability/Bioequivalence (BA/BE) Studies” finalized December 2012, European Directives 2001/20/EC and CT-3 Guideline, suspected adverse reaction means any AE for which there is a reasonable possibility that the medicinal product caused the AE. The phrase “reasonable possibility” means there is evidence to suggest a causal relationship between the AE and the medicinal product (see Section 9.3).

The following are examples of types of evidence that would suggest a causal relationship between the drug and the AE:

- A single occurrence of an event that is uncommon and known to be strongly associated with drug exposure (e.g., angioedema, hepatic injury, Stevens-Johnson Syndrome); or
- One or more occurrences of an event that is not commonly associated with drug exposure, but is otherwise uncommon in the population exposed to the drug (e.g., tendon rupture).

A suspected adverse reaction is considered “unexpected” if it is not listed in the Reference Safety Information in Section 6 of the K-877 Investigator’s Brochure or is not listed at the specificity or severity that has been described in the K-877 Investigator’s Brochure or the approved package insert of fenofibrate. Study sites will be provided with the current version of the fenofibrate package insert.

The Sponsor will report suspected unexpected serious adverse reactions (SUSARs) to Investigators, Competent Authorities, and IRB/ECs in an expedited manner according to national requirements. Fatal and life-threatening SUSARs will be reported within 7 calendar days of Day 0, where Day 0 is defined as the day on which the information containing the minimum reporting criteria is received by the Sponsor. All other SUSARs will be reported within 15 calendar days of Day 0. All cases will be unblinded for reporting purposes, as required.

## 10.6 REPORTING SERIOUS ADVERSE EVENTS, URGENT SAFETY ISSUES, AND SERIOUS BREACHES

### 10.6.1 Serious Adverse Events

#### 10.6.1.1 *Initial Reports*

All SAEs occurring from the time of informed consent until 30 days following the last administration of study drug must be reported to [REDACTED] within 24 hours of the knowledge of the occurrence (this refers to any AE that meets any of the aforementioned serious criteria). All SAEs that the Investigator considers related to study drug occurring after the 30 day follow-up period must be reported to the Sponsor.

To report the SAE, complete the SAE form electronically in the electronic data capture (EDC) system for the study. When the form is completed, [REDACTED] will be notified electronically and will retrieve the form. If the event meets serious criteria and it is not possible to access the EDC system, send an email to [REDACTED]

[REDACTED] and fax the completed paper SAE form to [REDACTED] [REDACTED] within 24 hours of awareness. When the EDC system becomes available, the SAE information must be entered within 24 hours.

Safety Contact Information: [REDACTED]

[REDACTED]

[REDACTED]

[REDACTED]

[REDACTED]

#### 10.6.1.2 *Follow-Up Reports*

The Investigator must continue to follow the patient until the SAE has subsided or until the condition becomes chronic in nature, stabilizes (in the case of persistent impairment), or the patient dies.

Within 24 hours of receipt of follow-up information, the Investigator must update the SAE form electronically in the EDC system for the study and submit any supporting documentation (e.g., patient discharge summary or autopsy reports) to [REDACTED] [REDACTED] via fax or email. If it is not possible to access the EDC system, refer to the procedures outlined above for initial reporting of SAEs. Written confirmation that these serious, unexpected, and related AEs have been submitted to the IRB/EC must be forwarded to KRI and kept in the Investigator files.

---

### **10.6.2 Urgent Safety Issues and Serious Breaches of Clinical Trial Regulation**

██████████ or any Investigator become aware of an actual or potential urgent safety issue or a serious breach of clinical trial regulations, the Medical Monitor and the Sponsor must be immediately contacted so that agreement can be made on appropriate urgent safety measures. An urgent safety issue is defined as:

- An immediate hazard to the health or safety of study patients participating in a clinical trial, or
- A serious risk to human health or potentially a serious risk to human health.

An urgent safety issue may include issues with an investigational drug or comparators, study procedures, intercurrent illness (including pandemic infections), concomitant medications, concurrent medical conditions, or any other issues related to the safe conduct of the study or that pose a risk to study patients.

In exceptional circumstances of imminent hazard and in order to safeguard the health or safety of individuals, █████ may take urgent safety measures before informing the Sponsor, but the Sponsor must be informed immediately after the hazard has been resolved.

## **11.0 STATISTICAL METHODS AND DATA ANALYSIS**

### **11.1 SAMPLE SIZE JUSTIFICATION**

Approximately 630 patients with fasting TG levels  $\geq 500$  mg/dL (5.65 mmol/L) and  $< 2000$  mg/dL (22.60 mmol/L) will be randomized in a 2:1 ratio into one of the following treatment groups: K-877 0.2 mg twice daily or identical matching placebo twice daily.

### **11.2 ANALYSIS POPULATIONS**

The study population will consist of male and female patients  $\geq 18$  years of age with fasting TG levels  $\geq 500$  mg/dL (5.65 mmol/L) and  $< 2000$  mg/dL (22.60 mmol/L) after washout from background lipid-altering therapy other than statins, ezetimibe, or PCSK9 inhibitors and with normal renal function. Stable therapy with statins, ezetimibe, or PCSK9 inhibitors will be allowed. The 40-week, active-controlled Extension Period population will consist of patients completing the 12-week placebo-controlled Efficacy Period. Patients in the 40-week, active-controlled Extension Period will be allowed to continue in the study even if the background lipid-altering therapy with statins, ezetimibe, or PCSK9 inhibitors requires adjustment.

#### **11.2.1 Full Analysis Set**

The Full Analysis Set (FAS) will consist of all randomized patients who take at least 1 dose of double-blind study drug and have a baseline TG measurement. The FAS Population is the primary analysis population. All efficacy analyses will be performed on the FAS Population.

#### **11.2.2 Per-Protocol Set**

The Per-Protocol Set will include all FAS patients for the 12-week Efficacy Period who complete the 12-week, placebo-controlled Efficacy Period without any major protocol

deviations and have valid baseline and Week 12 fasting serum TG measurements. Major protocol deviations will be pre-specified prior to unblinding the study. The Per-Protocol Set will be used to assess robustness of the primary analysis results during the 12-week Efficacy Period.

#### **11.2.3 Safety Analysis Set**

The Safety Analysis Set will include all randomized patients who receive at least 1 dose of randomized study drug. All safety analyses will be conducted on the Safety Analysis Set.

#### **11.2.4 Pharmacokinetic Analysis Set**

The PK Analysis Set will include all patients from the Safety Analysis Set who have at least 1 PK sample.

### **11.3 DEMOGRAPHIC/BASELINE INFORMATION**

Summary statistics will be provided by treatment group for demographics (e.g., age, gender, race, and ethnicity).

Baseline for TG, TC, HDL-C, non-HDL-C, LDL-C, and remnant cholesterol will be defined as the mean of Visit 4 (Day 1) and the preceding TG qualifying visit (either Visit 3 [Week -1] or Visit 3.1, if required) measurements. Baseline for all other efficacy and safety variables will be defined as Visit 4 (Day 1). If the measurement at this visit is missing, the last measurement prior to the first dose of randomized study drug will be used.

### **11.4 STUDY DRUG EXPOSURE, COMPLIANCE, AND CONCOMITANT THERAPIES**

Days of exposure to randomized study drug and study drug for the 12-week Efficacy Period and the 40-week Extension Period will be summarized with descriptive statistics by treatment for the Safety Analysis Set. Exposure in days is defined as the date of last dose of study drug minus the date of first dose of study drug plus 1.

Patient compliance with the study drug will be summarized by treatment group in each period.

Prior/concomitant medications will be coded with Anatomical Therapeutic Chemical (ATC) class and preferred term (defined by the most recent version of the World Health Organization Drug Dictionary) and summarized by ATC class and preferred term for each treatment group for the Safety Analysis Set.

## 11.5 ANALYSIS OF EFFICACY

### 11.5.1 Hypothesis Testing Procedure

In order to control the family-wise Type I error at a 0.05 level, a fixed sequential testing procedure will be implemented. In a hierarchical step-down manner, the primary endpoint will be tested first, followed by secondary endpoints, tested in the following hierarchical manner: percent change from baseline to Week 12 in a fixed sequence of (1) remnant cholesterol (calculated as TC – LDL-C – HDL-C), (2) HDL-C, (3) Apo A1, and (4) non-HDL-C. Each test is planned to be performed at a 0.05 significance level. Inferential conclusions about these efficacy endpoints will require statistical significance of the previous one.

[figure not shown]
For other efficacy endpoints, nominal p-values and 95% confidence intervals (CIs) will be presented, but should not be considered as confirmatory.

### 11.5.2 Analysis of Primary Efficacy Parameters

The primary efficacy analysis will be based on Hodges-Lehmann estimator with pattern-mixture model imputation based on the FAS. The pattern-mixture model will be used as the primary imputation method as part of the primary analysis for the percent change in fasting TGs from baseline to Week 12. This imputation model will include factors such as patient demographics, disease status, and baseline TG, as well as adherence to therapy. The imputation model will impute missing Week 12 TG values as follows:

- For patients who do not adhere to therapy and who do not have a Week 12 measurement, the missing data imputation method will use patients in the same treatment arm who do not adhere to therapy and have a Week 12 measurement; and
- If there are no patients in the same treatment arm who do not adhere to therapy and have a Week 12 measurement, missing Week 12 TG values will be imputed as follows:
  - For the K-877 arm, the treatment effect is considered washed out and baseline TG values will be used to impute the Week 12 TG values; and
  - For the placebo arm, missing Week 12 TG values will be imputed assuming missing at random, including patient demographics, disease status, and baseline and post-baseline efficacy data from the placebo arm.

After the multiple imputation step, each imputed dataset will be analyzed by the nonparametric Hodges-Lehmann method and the Hodges-Lehmann estimator and standard error will be combined to produce treatment difference estimate and 95% CI and p-value.

The primary efficacy analysis will be repeated on the Per-Protocol Set.

Summary statistics (number of patients, mean, standard deviation, median, minimum, maximum, 25th percentile, and 75th percentile) at baseline, each scheduled visit, and change and percent change in fasting TG from baseline to each scheduled visit will be provided.

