**Patient Population:**

The study population will consist of male and female patients  $\geq 18$  years of age with fasting TG levels  $\geq 500$  mg/dL (5.65 mmol/L) and  $< 2000$  mg/dL (22.60 mmol/L) after washout from background lipid-altering therapy other than statins, ezetimibe, or PCSK9 inhibitors and with normal renal function. Stable therapy with statins, ezetimibe, or PCSK9 inhibitors will be allowed. The 40-week, active-controlled Extension Period population will consist of patients completing the 12-week placebo-controlled Efficacy Period. Patients in the 40-week, active-controlled Extension Period will be allowed to continue in the study even if the background lipid-altering therapy with statins, ezetimibe, or PCSK9 inhibitors requires adjustment.

Number of Patients: Approximately 630 patients (420 patients receiving K-877; 210 patients receiving placebo/fenofibrate)	Number of Centers: Approximately 200 sites globally

Dose Levels:
 
12-week Efficacy Period
 
 
• K-877: 0.2 mg twice daily
 
• Placebo: twice daily
 
 
40-week Extension Period
 
 
• K-877: 0.2 mg twice daily/fenofibrate matching placebo: once daily
 
• Fenofibrate: 145 mg once daily/K-877 matching placebo: twice daily
 
	
Route of Administration:
 
Oral

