### 2.3 EXPLORATORY OBJECTIVE

### 2.4 PRIMARY EFFICACY ENDPOINT

The primary efficacy endpoint is the percent change in fasting TG from baseline to Week 12. Baseline for TG will be defined as the mean of Visit 4 (Day 1) and the preceding TG qualifying visit (either Visit 3 [Week -1] or Visit 3.1, if required) measurements.

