### **4.3 STUDY DRUG DISCONTINUATION CRITERIA**

It will be necessary to make a distinction between patients who prematurely discontinue study drug treatment and those who withdraw from the study for any reason.

If the patient discontinues study drug, the reason should be captured and could include the following:

1. The patient requests discontinuation of the study drug;
2. The patient begins to take any medication(s) that is contraindicated by the protocol;
3. The patient develops an AE that, in the opinion of the Investigator, would compromise the patient's safety to continue the study drug;
4. The patient meets any of the criteria specified in Section 4.6;
5. A female patient becomes pregnant during the study;
6. In the Investigator's judgment, it is in the patient's best interests; or
7. The patient is unblinded.

During the 12-week Efficacy Period, patients who discontinue study drug prematurely will remain in the study until Visit 7 (Week 12). However, patients who discontinue study drug during the 40-week Extension Period will be required to withdraw from the study and requested to complete the full panel of assessments scheduled for the Early Termination (ET) Visit (see Section 4.4). If a patient who has discontinued study drug fails to attend any follow-up appointments, reasonable efforts (telephone calls to family members or friends, e-mail contacts, etc.) will be made in order to encourage the patient to complete the study visits.

Although a patient is not obligated to give his/her reason for discontinuing study drug, the Investigator will make a reasonable effort to obtain the reason while fully respecting the patient's rights. The reason for discontinuation of study drug must be documented in the electronic case report form (eCRF). The Clinical Study Report (CSR) will include the reason(s) for discontinuation of study drug.

Patients will not be allowed to restart the study drug in the event of discontinuation; however, study drug may be restarted in cases of study drug interruption due to temporary use of prohibited medication(s) and AEs.

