#### 4.4 WITHDRAWAL CRITERIA

The patient has the right to withdraw from the study at any time. Nevertheless, in this study, every attempt will be made to prevent missing data and to obtain complete follow-up of all patients during the 12-week Efficacy Period. Investigators will be trained to minimize full withdrawals from the 12-week Efficacy Period wherever possible. Patients who discontinue study drug during the first 12 weeks are not required to withdraw from the study. These patients will be encouraged to remain in the study and asked to conduct the remaining study visits as outlined in the protocol through Visit 7 (Week 12). At a minimum, measurements of lipid parameters at key time points, particularly Visit 7 (Week 12), should be taken for all study patients, regardless of adherence to therapy or study protocol. If a patient fails to actively maintain contact with the Investigator, reasonable efforts (telephone calls to family members or friends, e-mail contacts, etc.) will be made in order to encourage the patient to complete the study visits.

If the patient withdraws from the study, the reason should be captured and could include the following:

1. The patient withdraws consent at any time or requests discontinuation of the study drug during the 40-week Extension Period;
2. The patient begins to take any medication(s) during the 40-week Extension Period that is prohibited by the protocol;
3. The patient develops an AE that, in the opinion of the Investigator, would compromise the patient's safety by continuing in the study;
4. The patient meets any of the criteria specified in Section 4.6 during the 40-week Extension Period;
5. A female patient becomes pregnant during the study;
6. The patient fails to comply with protocol requirements or study-related procedures if, in the opinion of the Investigator or the Sponsor, the non-compliance will significantly compromise data interpretation or safety;
7. In the Investigator's judgment, it is in the patient's best interests;
8. Violation of the protocol inclusion and exclusion criteria is discovered, if, in the opinion of the Investigator or the Sponsor, the violation will significantly compromise data interpretation or safety;
9. The patient is unblinded during the 40-week Extension Period; or
10. The Sponsor or the regulatory authority terminates the study.

Patients who choose to withdraw consent will be asked to document withdrawal of consent in writing.

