1. INTRODUCTION

The statistical analysis plan, version 2.0, for study with protocol number K-877-301 was finalized on June 21, 2019. The study was finished with the database locked on August 23, 2019. The treatment code was unblinded on August 26, 2019. Due to issue in coding process for prior and concomitant medications coding and medical history coding in electronic data capture system, the database was corrected and locked again on September 11, 2019.

The study results were reviewed. After the systemic review, the decision was made to perform the post-lock data analysis change or clarification as described in this document.

Summary of changes:

- The primary imputation method in the SAP did not take into account the scenario of imputing missing data when observed data had a value of 0. We have specified all scenarios for the primary imputation method.
- The secondary efficacy endpoint, where data value of 0 is observed at baseline, will additionally include analysis for ‘change from baseline to week 12’ given percent change not being calculable for such lab parameters. However, for these lab parameters, analysis of percent change from baseline to week 12 will be performed using data where percent change from baseline is available.

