4. PRIMARY IMPUTATION METHOD

For the main analysis of the primary efficacy variable, missing Week 12 endpoint will be imputed using the pattern mixture model using the fully conditional specification method. This imputation method will include factors such as patient demographics, disease status, and baseline values. The imputation method was specified in the SAP Appendix 1, pages 25, 26 and 27.

It was found after database lock that there was an error imputing data with a value of 0 as the pattern mixture model using the fully conditional specification method utilized log transformation of the observed values. The parameters mentioned in section 2.1 of this document resulted in imputation error because of log transformation of 0 values. After reviewing the methodology in SAP, it was decided that this scenario would be handled using the predictive mean matching method as an extension to the pattern mixture model of imputation.

Below is a summary of description of the imputation using the predictive mean matching method:

In addition to following the same description of steps in Appendix 1 (in Pages 25-27) of the SAP version 2.0, any lab parameter with a 0 value at baseline or week 12 will utilize the following SAS code to include the predictive mean matching method to impute missing data.

Step II a.

```
PROC MI DATA= DATA21a OUT=IMOUT1a
  MINIMUM=0 SEED=68756 NIMPUTE=100 ROUND=1E-10;
  VAR AGE SEX ETHNICITY COUNTRY BMI SBP DBP EGFR STATIN WEEK12; CLASS
  SEX ETHNICITY COUNTRY STATIN;
  FCS REGPMM; /* fully conditional specification method with predictive mean matching
  method.*/
  RUN;
```

Step II b.

```
PROC MI DATA=DATA22 OUT=IMOUT22
  MINIMUM=0 SEED=63546 NIMPUTE=100 ROUND=1E-10;
  VAR AGE SEX ETHNICITY COUNTRY BMI SBP DBP EGFR STATIN BASE WEEK 4
  WEEK8 WEEK12;
  CLASS SEX ETHNICITY COUNTRY STATIN;
  FCS REGPMM; /*fully conditional specification method with predictive mean matching
  method*/
  RUN;
```

Step III.

```
PROC MI DATA= DATA21c OUT=IMOUT1c
    MINIMUM=0 SEED=745369 NIMPUTE=100 ROUND=1E-10;
BY TRT;
VAR AGE SEX ETHNICITY COUNTRY BMI SBP DBP EGFR STATIN BASE WEEK4
    WEEK8 WEEK12;
CLASS SEX ETHNICITY COUNTRY STATIN;
FCS REGPMM; /*fully conditional specification method with predictive mean matching
method*/
RUN;
```

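### Does the unstated Hodges-Lehmann standard error leave the primary 95% confidence interval too narrow?

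*Protocol*

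**What the plan says.** The endpoint is on the raw percentage scale: "The primary efficacy endpoint is the percent change in fasting TG from baseline to Week 12" (protocol section 2.4). About 630 patients are randomized 2:1, 420 to K-877 and 210 to placebo (synopsis, Number of Patients), stratified by country and statin use (section 6.1). For the primary analysis, section 11.5.2 says that "each imputed dataset will be analyzed by the nonparametric Hodges-Lehmann method and the Hodges-Lehmann estimator and standard error will be combined". It gives no formula for the standard error and does not name the combining rule; the synopsis repeats the same text.

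The document supplied as the SAP is an addendum written after database lock. Its introduction records that "The statistical analysis plan, version 2.0, for study with protocol number K-877-301 was finalized on June 21, 2019". On the primary method it covers imputation only: "The imputation method was specified in the SAP Appendix 1, pages 25, 26 and 27", followed by code for laboratory parameters with zero values (for example "MINIMUM=0 SEED=68756 NIMPUTE=100 ROUND=1E-10"). Its section 3 says that the changes do not affect the primary endpoint or the hierarchical secondary endpoints.

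Two provisions bear on spread in the K-877 arm. Patients who stop drug in the Efficacy Period stay in follow-up to Week 12, and section 4.4 asks that key lipid measurements "should be taken for all study patients, regardless of adherence to therapy or study protocol". Missing Week 12 values in non-adherent patients are drawn from non-adherent patients in the same arm; the K-877 arm falls back on the baseline value only if there are no such donors (section 11.5.2).

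**The concern.** The Hodges-Lehmann estimator has no single standard error. The conventional one takes the Wilcoxon-inversion interval and divides its width by 2 × 1.96, which is correct if the two distributions have the same shape and differ only in location. On a percent-change scale that is doubtful for an effective drug. If K-877 multiplies triglycerides by a constant, its spread on that scale shrinks by the same factor. The arm with the smaller spread is then also the larger arm, which is the combination in which a shift-model standard error is too small.

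At stake is the stated precision of the main treatment difference. If a hierarchical secondary endpoint fails the normality check, section 11.5.3 falls back on the same estimator, so the question would reach those intervals too. The test of identical distributions is not at stake, because the shift-model variance is correct there.

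**Working it through.** **Inputs from the documents.** m = 420 (K-877) and n = 210 (placebo), consistent with 630 × 2/3 and 630 × 1/3; raw percent change; a 95% CI. No SD, effect size, missing-data rate, standard error or interval width is visible, so apart from that split there is no figure of the plan's own to reproduce. Everything about spread and effect below is assumed.

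**Formula.** With the arms centred at zero Hodges-Lehmann shift, the large-sample ratio of the shift-model SE to the true SE is

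sqrt{ [(1/12)(1/m + 1/n)(m+n+1)/(m+n)] / [Var(F_P(K))/m + Var(F_K(P))/n] }.

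The numerator inside the root is (1/12)(1/420 + 1/210)(631/630) = 0.00059618. Coverage of the nominal 95% interval is 2Φ(1.96 × ratio) − 1.

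**Hand check, normal data.** Let r = SD(K-877)/SD(placebo). Then Var(F_P(K)) = arcsin(r²/(1+r²))/(2π) and Var(F_K(P)) = arcsin(1/(1+r²))/(2π).

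- r = 1: both are 1/12, so the ratio is 1.00.
- r = 0.5: the variances are 0.03205 and 0.14758. The denominator is 0.03205/420 + 0.14758/210 = 0.00077908. The ratio is sqrt(0.00059618/0.00077908) = 0.875, so the SE is 12.5% too small and coverage is 91.4%.
- r = 1.5: the variances are 0.12169 and 0.04978. The denominator is 0.00052679 and the ratio is 1.064, so the SE is 6.4% too large.

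No value near 12% is a bound. At r = 0.4 the SE is 15.8% too small, and as r approaches 0 the shortfall approaches 29%. At r = 2 it is 8.8% too large.

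**Percent change from lognormal data.** Placebo log-SD is 0.5. "Off effect" means K-877 patients with no drug effect. Entries are the SE shortfall, with coverage in brackets; a negative shortfall means that the SE is too large.

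| K-877/placebo log-SD, off effect | 30% drop | 40% drop | 50% drop |
|---|---|---|---|
| 0.8, none | 10.7% (92.0) | 13.1% (91.1) | 15.6% (90.2) |
| 1, none | 6.7% (93.3) | 9.4% (92.4) | 12.4% (91.4) |
| 1, 10% | 5.6% (93.6) | 7.8% (92.9) | 10.1% (92.2) |
| 1.25, 10% | 1.5% (94.6) | 3.9% (94.0) | 6.5% (93.3) |
| 1.5, 10% | −1.6% (95.4) | 0.7% (94.8) | 3.4% (94.2) |

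Separate runs agree to about 0.3 points. The second row matches the normal results at r = 0.7, 0.6 and 0.5 (6.7, 9.5 and 12.5%), as it should when a proportional drop scales the spread by the same factor.

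**With multiple imputation.** Assume that 10% of patients are non-adherent, and that Week 12 is missing in 50% of these and in 3% of the rest: 0.10 × 0.50 + 0.90 × 0.03 = 7.7% missing. Same-arm, same-adherence donors and Rubin's rules (20 imputations, equal log-SD) give shift-model coverage of 94.4, 92.2 and 92.2% for drops of 30, 40 and 50%. A placement-based SE gives 95.7, 94.1 and 94.6%. Simulation error is about 0.7 points. Covariates and Week 4 and 8 values were not modelled.

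**With prognostic strata.** Assume that the strata explain 20% of the variance (40% drop, equal log-SD, no off-effect patients). The shift-model SE is then 0.99 of the true SD, with 94.2% coverage. The remedies that resample or rank by arm alone over-cover: 98.0% for the bootstrap (250 trials) and 96.6% for the placement-based SE. A bootstrap within arm and stratum covers 94.0%.

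**Effect on the conclusion.** In the imputation runs the treatment difference lay about 6 (30% drop) to 11 (50% drop) true SEs from zero, against a threshold of 1.96.

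**The case for a change.** The strongest case for acting is that this standard error is the only source of the primary interval and p-value. Raw percent change, 2:1 allocation and an expected lowering of triglycerides all point towards a shortfall, and stating the formula costs one sentence. If the formula assumes a pure shift, one labelled sensitivity interval would show whether it matters.

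Part of this stands. The two available documents do not give the formula, and the conditional arithmetic reproduces. Anyone reporting the interval should know which standard error was used.

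The rest does not amount to a defect. Leaving a variance formula to the SAP is ordinary practice, and an addendum about zero values is not where one would look for it. The size depends on a shift-model SE having been chosen, on a near-proportional effect and on K-877 log-spread not much above placebo; none of these can be checked here. Retained off-drug patients and prognostic strata both pull the shortfall down. The baseline fallback is weaker support, because it applies only when the K-877 arm has no observed non-adherent donors. The sensitivity interval would come after unblinding on August 26, 2019, could not replace the planned one, and has no obviously best variance method: the arm-only versions are conservative in exactly the setting where the planned SE needs no repair.

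**Conclusion.** No change to the plan. What is missing is a detail that SAP version 2.0 would normally hold and that an analyst can read off there; it is a point to confirm, not a demonstrated omission. If that formula allows unequal spread, nothing remains. If it assumes a pure shift, the interval could be about 7 to 12% too narrow (equal log-spread, log-SD 0.5, 30 to 50% drop), more if K-877 spread is lower still, and about right if K-877 response is more variable or the strata are prognostic. All of those inputs are assumptions. An effect some 6 to 11 standard errors from zero under the same assumptions would not be overturned by an error of that size, so an added post-unblinding interval is optional and offers little gain.
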